1. INTRODUCTION

Revision Chronology:				
2012N154810_00	22-Aug-2013	Original		
2012N154810_01	04-Oct-2013	Amendment 01		
2012N154810_02	14-Jan-2014	Amendment 02		
2012N154810_03	01-Apr-2014	Amendment 03		
2012N154810_04	31-Aug-2015	Amendment 04		
2012N154810_05	03-Dec-2015	Amendment 05		
2012N154810_06	12-Sep-2017	Amendment 06		

The purpose of this reporting and analysis plan (RAP) is to describe the analyses to be included in the Clinical Study Report for Protocol 116027:

2.1. Changes to the Protocol Defined Statistical Analysis Plan

Changes from the originally planned statistical analysis specified in the protocol are outlined in Table 2.

	otocol	Reporting & Analysis Plan		
Statistical Analysis Plan		Statistical Analysis Plan	Rationale for Changes	
•	Partial prothrombin time (PTT) is collected	 Activated partial prothrombin time (aPTT) time is analyzed 	aPTT was collected instead of PTT	
•	Section 8.1.3 states that for the primary analysis of the additional efficacy and biomarkers, the baseline will be defined as study Day 0 of the original parent study. Additionally, for some of the endpoints, a secondary analysis will be performed by defining the baseline as Day 0 of the BEL116027 study.	• The baseline for each endpoint is defined per Section 6.1 of the protocol.	The protocol was inconsistent in the definition of baseline. See RAP Section 5.3 for clarification	
•	Immunogenicity is listed as a secondary endpoint in Protocol Section 6.1.2., but as an exploratory laboratory parameter in the Time and Events table.	 Immunogenicity is defined as a secondary endpoint. 	 The protocol was inconsistent, so the correct category was used in the RAP. 	
•	Renal flares are not listed as an endpoint in Protocol Section 6.1.2 nor described in Protocol Section 8, but are defined in Protocol Section 6.1.4	 Renal flares are included as an exploratory endpoint in RAP Section 2.2. 	 The protocol was inconsistent, so the endpoint was correctly specified in the RAP. 	
•	The definition of renal flare contained a typographical error and referenced an increase rather than a decrease in GFR. This was corrected in a note to file.	 The RAP specifies the correct definition, referencing a decrease in GFR. 	The protocol was incorrect.	
•	Protocol Section 6.1.3 lists percent change in PGA.	 The RAP specifies change from baseline in PGA instead. 	Change from baseline is more clinically relevant and interpretable, particularly in the case of low baseline scores.	
•	Protocol Section 6.1.2 lists one time interval for percent change in B-cell subsets from Week 24, i.e., Week 24 to 52.	 In addition to this, the RAP specifies percent change from Week 24 to 32 and Week 24 to 40. 	The additional time intervals facilitate interpretation of the changes following the treatment holiday phase.	
•	The protocol Section 6.1.2 does not list the CD19+ B-cell subset. The protocol Section 6.1.3 Other Endpoints includes percent change in prednisone dose and percent of subjects with prednisone dose reduced to <7.5mg/day from ≥7.5mg/day	 The RAP adds the CD19+ B-cell subset. These two exploratory endpoints were not analysed 	 This subset is collected and clinically important. The two secondary prednisone endpoints (Protocol Section 6.1.2) will be analysed as they are most descriptive in that they assess daily prednisone use. Given the reduced sample size from 	

Table 2Changes to Protocol Defined Analysis Plan

[figure not shown]
Protocol	Reporting & Analysis Plan	
Statistical Analysis Plan	Statistical Analysis Plan Rationale for Changes	
		the original protocol, these two endpoints allow sufficient evaluation of the impact of the treatment holiday.
 Section 6.1.2 lists percent change from baseline in B-Cells, immunoglobulins and auto- antibodies 	 Change from baseline will also be presented for these parameters. 	 Change from baseline added based on regulatory feedback on other studies in the belimumab development program.

2.2. Study Objective(s) and Endpoint(s)

Objectives	Endpoints
Primary Objectives	Primary Endpoints
 Characterize the efficacy of a 24-week withdrawal followed a 28-week reintroduction of intravenous belimumab thera compared with uninterrupted intravenous belimumab thera for 52 weeks in subjects with SLE disease activity receivin belimumab 10 mg/kg plus standard of care, as measure by time to first flare. 	by ipy low g
Secondary Objectives	Secondary Endpoints
• Evaluate the rate of any flare	 Rate of any SLE Flare Index flare per subject year. Time to first SLE Flare Index severe flare.
 Assess safety. 	 Adverse events AESI Laboratory parameters Vital signs
Assess SLE disease activity.	 Number of subjects in the treatment holiday and long-term discontinuation group with evidence of rebound (defined as a SELENA SLEDAI score during the first 24 weeks that exceeds the baseline SELENA SLEDAI score in the subjects' respective original parent study). SELENA SLEDAI scores change from baseline.
Assess immunogenicity.	Response (Negative, Transient Positive, Persistent Positive) by Visit and Across All Visits
 Assess markers of autoimmuresponse (e.g., immunoglobulins, compleme 	anti-dsDNA, ANA, C3, and C4.

Objectives	Endpoints	
	(CD19+, CD20+, CD20+/27+ memory, CD20+/27– naïve, CD20+/69+ activated, CD20+/138+ plasmacytoid, CD19+/27BRIGHT/38BRIGHT SLE subset and CD20-/138+ plasma cells) at Weeks 0, 8, 16, 24, 32, 40 and 52 and from Weeks 24 to 52.	
 Assess changes in corticosteroid use. 	 Number of days of daily prednisone dose ≥7.5 mg/day and/or increased by 25% from Day 0 of this study to Week 24, from Day 0 of this study to Week 52, and from Week 24 to Week 52. 	
	 Number of days of daily prednisone dose ≤7.5 mg/day and/or decreased by 25% from Day 0 of this study to Week 24, from Day 0 of this study to Week 52, and from Week 24 to Week 52. 	
Exploratory/Other	Exploratory/Other Endpoints	
	Time to first renal flare	
	 Time to first renal flare among subjects with baseline proteinuria >0.5g/24hr equivalent 	
	Change from Baseline in PGA	
	 Change and percentage change from Baseline in BLyS Protein 	
	SLICC/SDI	
	Change from Baseline	

2.3. Study Design

Overview of Study Design ar	Overview of Study Design and Key Features	
	this long-term safety data to regulatory authorities in the initial BLA and other marketing authorization submissions). Additional interim analyses may be required to support subsequent safety updates to regulatory authorities. No interim analyses were conducted.	
Sample Size	• The total target sample size was 71 subjects and 80 were enrolled. The target sample size for subjects in the treatment holiday and control groups was 10 (12 enrolled) and 26 (29 enrolled) subjects respectively. A target sample size of 35 (39 enrolled) subjects in the long-term discontinuation group was anticipated.	

Note: Subjects from China participated in BEL113750 OL phase rather than in BEL114333, and were therefore eligible to enter BEL116027 from BEL113750 OL, per a China country-specific protocol amendment 01.

2.4. Statistical Hypotheses / Statistical Analyses

Since this is a non-randomized study, results will be descriptive only, and any comparisons are not intended to be inferential.

3. PLANNED ANALYSES

3.1. Interim Analyses

The protocol indicated that an interim analysis of the data in this trial may be performed to support a submission to regulatory authorities relating to marketing authorization (e.g., to summarize and submit this long-term safety data to regulatory authorities in the initial BLA and other marketing authorization submissions). Additional interim analyses may be required to support subsequent safety updates to regulatory authorities. No interim analyses were conducted.

The SRT performs in stream adjudication of subject-level safety data for Adverse Events of Special Interest (AESIs; serious and non-serious) in accordance with the GSK Standard Operating Procedures (SOPs) and the belimumab Program Safety Analysis Plan (PSAP). AESIs include malignancy; serious hypersensitivity and post-infusion systemic reactions; potential opportunistic infections; other infections of interest but not generally considered opportunistic i.e. Mycobacterium Tuberculosis and Herpes Zoster; suicide/self-injury; and fatalities.

AESIs are flagged in the clinical trial database, according to SRT adjudication. The SRT performs a periodic review of instream study data (at least every 6 months), reviewing the cumulative incidence of AEs, SAEs, and adjudicated AESIs. These periodic reviews of cumulative adverse event incidence are compared with previous SRT reviews and where appropriate, the pivotal SLE pooled data to assess for any new safety signals.

3.2. Final Analyses

The final planned primary analyses will be performed after the database cleaning activities have been completed and final database release and database freeze has been declared by Data Management:

database cleaning activities have been completed and final database release and database freeze has been declared by Data Management.

In this open-label, non-randomized study, for dispensing of study drug, randomisation codes have been distributed according to RandAll NG procedures.

Population	Definition / Criteria	Analyses Evaluated	
Screened	Comprises all subjects who enroll in the study, including screen failures	 Study population 	
Intent-To-Treat	Comprises all subjects who enroll in the study,	Study population	
	excluding screen failures.	Efficacy	
		Safety	
		Biomarker	
РК	Comprises all subjects included in the ITT population for whom at least one post belimumab treatment PK sample was obtained and analyzed.	• PK	

4. ANALYSIS POPULATIONS

1. NOTES:

 Please refer to Appendix 11: List of Data Displays which details the population to be used for each display being generated.

4.1. Protocol Deviations

Important protocol deviations (including deviations related to study inclusion/exclusion criteria, conduct of the trial, patient management or patient assessment) will be identified in the Protocol Deviation Management Plan (PDMP).

Protocol deviations will be tracked by the study team throughout the conduct of the study in accordance with the PDMP.

- Data will be reviewed prior to freezing the database to ensure all important deviations are captured and categorised on the protocol deviations dataset.
- This dataset will be the basis for the summaries and listings of protocol deviations.

Important protocol deviations (including deviations related to study inclusion/exclusion criteria, conduct of the trial, patient management or patient assessment) will be summarised and listed.

5. CONSIDERATIONS FOR DATA ANALYSES AND DATA HANDLING CONVENTIONS

5.1. Study Treatment Descriptors

Treatme	Treatment Group Descriptions		
	RandAll NG Data Displays for Reporting		
Group Code	Group Description	Description	Order ^[1]
3	Long Term Discontinuation Group	Long-term Discontinuation	1
2	Control Group	Treatment Control	2
1	Treatment Holiday Group	Treatment Holiday	3

NOTES:

1. Order represents treatments being presented in TFL, as appropriate. Some Tables will only present TC and TH groups.

2. In applicable data listings, Screen Failures will be presented first followed by LTD, TC and TH.

5.2. Parent Studies

Subjects were eligible to enter BEL116027 from one of four continuation studies, having entered the continuation study from a respective parent study. The possible study participation sequences are as follows:

Parent Study	Continuation Study	Subjects
BEL113750 DB1	BEL113750 OL1	Subjects from China
BEL112341 ²	BEL114333	Some subjects from Japan
BEL113750	BEL114333	Subjects from Korea and some subjects from Japan
BEL110751	BEL112233 (C1066)	Subjects from US
LBSL02	LBSL99 (BEL112626)	Subjects from US

1. BEL113750 was both the parent and continuation study number for subjects enrolled in China.

 Subjects from Japan who participated in study BEL112341 were eligible to enrol into the BEL114333 continuation phase per a BEL114333 protocol amendment, to allow them continued access to study agent until belimumab was commercially available in Japan.

5.3. Baseline Definitions

5.3.1. Baseline Definitions¹

The baseline (BL) definition is dependent upon the endpoint being analyzed.

• For the SELENA SLEDAI (including rebound), immunoglobulins, autoantibodies, complement, BLyS and B-cell endpoints, baseline is defined as the Day 0 assessment in the subject's respective parent study, prior to exposure with study treatment (whether placebo or belimumab). Baseline data for these

parameters will be extracted from the ADaM data sets from the double blind study (LBSL02, BEL110751, BEL113750 or BEL112341) from which the patients are enrolled.

- For the SLE flares, SLE severe flares, SLICC, prednisone (7 day average prior to Day 0), PGA, and immunogenicity², endpoints, baseline is the Day 0 assessment in BEL116027.
- For other endpoints, baseline is the Day 0 assessment in BEL116027².

¹Feeder study BEL114333 database had not yet completed at the time of BEL116027 Last Patient Last Visit. Consequently, baseline data for BEL114333 patients has not been fully cleaned when extracted from that study's database for reporting.

²Assessments covered for both Day 0 in BEL116027 and the Exit/Follow-up visit of the feeder continuation studies were only to be performed once and were to be recorded in the appropriate case report forms for each study. For Day 0 values not recorded in BEL116027 CRF but exist in the feeder study, the data will be extracted from the appropriate feeder study for inclusion in analysis

In the displays, the baseline value/visit will be denoted as Baseline.

See Section 13.4.1 for a diagram depicting the baseline definitions and phases.

Definition	Reporting Details
Change from Baseline	= Post-Dose Visit Value – Baseline
% Change from Baseline	= 100 x [(Post-Dose Visit Value – Baseline) / Baseline]
Maximum Change from Baseline	= Calculate the change from baseline at each given timepoint
	and determine the maximum change

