6.1.2. Secondary Endpoints

The secondary endpoints are:

- Rate of any SLE Flare Index flares.
- Time to first severe SLE Flare Index flare.
- Number of subjects in the treatment holiday and long-term discontinuation group with evidence of rebound (defined as a SELENA SLEDAI score during the first 24 weeks that exceeds the baseline SELENA SLEDAI score in the original parent study.
- Number of subjects with confirmed true positive belimumab anti-drug antibodies (ADA) by the end of the study.
- Percentage change from baseline in:
 - Total serum immunoglobulin (IgG, and other isotypes: IgM and IgA)
 - Autoantibodies (anti-dsDNA, ANA), and complement (C3, C4)
- Percent change in absolute B cell subsets (CD20+, CD20+/27+ memory, CD20+/27naïve, CD20+/69+ activated, CD20+/138+ plasmacytoid, CD19+/27BRIGHT/38BRIGHT SLE subset and CD20-/138+ plasma cells) at Weeks 0, 8, 16, 24, 32, 40 and 52 and from Weeks 24 to 52.
- Absolute change in SELENA SLEDAI score.
- Number of days of daily prednisone dose ≥7.5 mg/day and/or increased by 25% from Day 0 of this study to Week 24, from Day 0 of this study to Week 52, and from Week 24 to Week 52.
- Number of days of daily prednisone dose ≤7.5 mg/day and/or decreased by 25% from Day 0 of this study to Week 24, from Day 0 of this study to Week 52, and from Week 24 to Week 52.

Note: baseline is the time before any treatment with belimumab, which was Day 0 of the original parent studies that fed into the 3 continuation studies from which subjects were recruited into this study. When Day 0 is used in relation to endpoints, this refers to Day 0 of this study.

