8.1.3. Analysis of Additional Efficacy Endpoints

For the primary analysis of the additional efficacy and biomarkers, the baseline will be defined as study Day 0 of the original parent study. Additionally, for some of the endpoints, a secondary analysis will be performed by defining the baseline as Day 0 of the BEL116027 study.

The major analysis of the additional efficacy and biomarkers will include descriptive tabulation of secondary endpoints by treatment group according to the treatment group they are assigned to in the BEL116027 study.

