5.3.2. Derivations and Handling of Missing Baseline Data

NOTES:

 Unless otherwise specified, the baseline definitions specified in Section 5.3.1 Baseline Definitions will be used for derivations for endpoints / parameters and indicated on summaries and listings.

 Unless otherwise stated, if baseline data is missing no derivation will be performed and baseline will be set to missing.

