7. EFFICACY ANALYSES

For all efficacy analyses, results for the TH group will be presented for the treatment holiday (TH) and re-start (RS) phases separately.

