7.2.2.4. SELENA SLEDAI Scores

Summary statistics for the change from baseline in SELENA SLEDAI scores will be presented at each visit in the 52-week treatment phase.

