13.11.5. Efficacy Tables

Efficacy	: Tables			
No.	Population	Title	Programming Notes	Priority Headline Results denoted by H
Flares				
2.1.	ITT	Time to First SFI Flare to Week 52	Primary endpoint	Н
2.2.	ITT	SFI Flares per Subject-year from Day 0 to Week 52	Secondary endpoint	
2.3.	ITT	Time to First SFI Severe Flare to Week 52	Secondary endpoint	Н
2.4.	ITT	Time to First Renal Flare to Week 52	Exploratory endpoint	Н
2.5.	ITT	Time to First Renal Flare to Week 52 [1] Among Subjects with Baseline Proteinuria >0.5g/24hr Equivalent	Exploratory endpoint	
Reboun	d and SELENA-	SLEDAI		
2.6.	ITT	SELENA SLEDAI Rebound (LOCF) (52-Week Treatment Phase)	Secondary endpoint	Н
2.7.	ITT	SELENA SLEDAI Change from Baseline (LOCF) (52-Week Treatment Phase)	Secondary endpoint	
PGA		·		
2.8.	ITT	PGA Change from Baseline (52-Week Treatment Phase)	Other/exploratory endpoint	
Prednis	one			
2.9.	ITT	Number of Days of Daily Prednisone Dose >=7.5 mg/day and/or Increased by 25%	Secondary endpoint	
2.10.	ITT	Number of Days of Daily Prednisone Dose <=7.5 mg/day and/or Decreased by 25%	Secondary endpoint	

Efficacy	Efficacy: Tables				
No.	Population	Title	Programming Notes	Priority Headline Results denoted by H	
2.11.	ITT	Prednisone Percent Change from Baseline (52-Week Treatment Phase)	Other/exploratory endpoint		
2.12.	ITT	Prednisone Reduced to <= 7.5 mg/day by Visit (DO/TF=NR) among Subjects with Baseline Prednisone Dose > 7.5 mg/day (52-Week Treatment Phase)	Other/exploratory endpoint		

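### No planned summary gives within-subject change in SELENA SLEDAI, complement or autoantibodies over the 24-week holiday, because their only baseline is the parent-study value

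*SAP*

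**What the plan says.** SAP 5.3.1 assigns SELENA SLEDAI, complement and autoantibodies to the parent-study baseline: "For the SELENA SLEDAI (including rebound), immunoglobulins, autoantibodies, complement, BLyS and B-cell endpoints, baseline is defined as the Day 0 assessment in the" subject's parent study. SAP 5.3.2 applies this throughout unless otherwise specified: "the baseline definitions specified in Section 5.3.1 Baseline Definitions will be used for derivations for endpoints / parameters". It agrees with the note in protocol 6.1.2, where "baseline is the time before any treatment with belimumab, which was Day 0 of the original parent studies".

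Protocol 8.1.3 went further. It took the parent baseline as primary and added that "for some of the endpoints, a secondary analysis will be performed by defining the baseline as Day 0 of the BEL116027 study", without naming the endpoints. SAP 2.1, Table 2, replaces this with one baseline per endpoint and gives as its reason: "The protocol was inconsistent in the definition of baseline".

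The planned summaries follow from that choice:

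- SELENA SLEDAI (SAP 7.2.2.4): "Summary statistics for the change from baseline in SELENA SLEDAI scores will be presented at each visit" of the 52-week phase. The other summary is rebound, a score above the parent score in the first 24 weeks (SAP 7.2.1.3).
- Autoantibodies and complement (SAP 11.1.2.2): change and percent change from the parent baseline at each visit, Day 0 included, plus shifts.
- Flares, PGA, SLICC, prednisone and immunogenicity use BEL116027 Day 0 (SAP 5.3.1). B cells have a Week 0 row and also change from Week 24 (SAP 11.1.2.1).

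SAP 7 further states that "results for the TH group will be presented for the treatment holiday (TH) and re-start (RS) phases separately".

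**The concern.** Disease activity and autoimmune markers are secondary objectives, and the study is about what happens when belimumab is withdrawn for 24 weeks. A change measured from before belimumab was ever given combines two things: the response gained before this study and whatever happened during the holiday. Presenting the holiday and re-start phases separately does not separate them, because both phases are measured from the same earlier point.

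The study is descriptive, with 12 holiday, 29 control and 39 long-term discontinuation subjects enrolled (SAP 2.3). The summaries are therefore the result for these measures, and no test is available to supplement them.

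**Working it through.** No figure in the plan bears on this point, so there is none to reproduce. The check is of the planned displays, followed by arithmetic on the entry criteria.

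**1. Displays.** In SAP 13.11.5, 13.11.6, 13.11.11 and 13.11.12, the relevant items are Tables 2.6 and 2.7, Tables 5.1 to 5.10, and Figures 2.3 and 5.1 to 5.4. All are titled as rebound or as change, percent change or shift from Baseline. None is titled as change from BEL116027 Day 0. SAP 7.2.3 uses the Day 0 SELENA SLEDAI score only to split the rebound analysis at 3.

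**2. SELENA SLEDAI.** Let P be the parent score and D the Day 0 score. Holiday and control subjects enter with D of 0 to 3 (protocol 4.2). BEL113750 is described as enrolling P of 8 or more (protocol Appendix 7, Section 3.2). A Week 24 score equal to P is a rise of P − D from Day 0. It is tabulated as P − P = 0 and is not rebound, which needs at least P + 1.

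| P | Rise from Day 0 tabulated as zero change (P − 3 to P) | Rise needed for rebound (P − 2 to P + 1) |
|---|---|---|
| 6 (assumed) | 3 to 6 | 4 to 7 |
| 8 (BEL113750 minimum) | 5 to 8 | 6 to 9 |
| 12 (assumed) | 9 to 12 | 10 to 13 |

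For a BEL113750 subject, change from baseline is already 3 − 8 = −5 or lower at Day 0. Any such subject can therefore rise 5 points without showing a positive change, and rebound takes at least 6. Some subjects from Japan have BEL112341 as parent study (SAP 5.2). No score floor is given for it, hence the assumed row P = 6.

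**3. What subtraction recovers.** Take six constructed subjects whose changes from parent at Day 0 are −11, −10, −9, −8, −7 and −6 (mean −8.5, SD 1.87). In case A each rises 3 points by Week 24. In case B the same Week 24 values are attached in reverse order. Week 24 change from parent has mean −5.5 and SD 1.87 in both cases.

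- Case A: every within-subject change is +3; mean 3.0, SD 0, and 6 of 6 rise by 3 or more.
- Case B: the changes are 8, 6, 4, 2, 0 and −2; mean 3.0, SD √(70/5) = 3.74, and 3 of 6 rise by 3 or more.

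The tabulated rows are identical, so the mean is recoverable but the spread and the number worsening are not. For serology even the mean is approximate, because data are summarised as observed (SAP 11.1.4) and the two rows may hold different subjects.

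**4. Percent change and shift, illustrated for C3.** Assume 70 (parent), 100 (Day 0) and 85 (Week 24) mg/dL.

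- From parent: +30/70 = +42.9% at Day 0 and +15/70 = +21.4% at Week 24. The fall of 15 is visible, but the percent rows differ by 21.4 points.
- From Day 0: −15/100 = −15.0%.
- With the SAP cut-off of 90 (13.6.6.1), the shift to Week 24 is low-to-low from parent and normal-to-low from Day 0.

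**5. Is there a Day 0 row for SELENA SLEDAI?** SAP 13.4.1 places Day 0 assessments in the pre-study phase, but SAP 11.1.2.2 plans a Day 0 row for serology under that same rule. SAP 13.3.3 lists visit 20 (Study Day 1) among the 52-week visits. A row is likely but not explicit, and the shells are not in the SAP (13.12).

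**The case against.** The parent baseline is prespecified in protocol 6.1.2, and the SAP records its departure from 8.1.3 openly. A reader might infer that the SAP broke a commitment to analyse these measures from Day 0. The documents do not support that, because 8.1.3 names no endpoints.

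A reader might also infer that worsening during the holiday would go unseen. That is too strong. The SLE Flare Index uses SELENA SLEDAI change from the most recent assessment (protocol 6.3.1.3). SAP 13.6.3 checks this criterion by program and counts a rise of at least 3 from the previous visit. A rise of 5 or more from Day 0 would escape the primary endpoint only if every step between visits stayed below 3 and no other flare criterion was met. PGA change is taken from Day 0. Listings 44 and 50 give individual SELENA SLEDAI and serology results, which is practical with 12 holiday subjects. For complement, holiday and control subjects had to enter with normal C3 and C4. A by-visit count of low values may therefore already show loss of normal levels, depending on the layout of Table 5.10.

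All of this stands and limits the impact. It does not supply the missing summary: flare and PGA are different measures, and a listing is not a tabulated change.

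Nor should the immunoglobulin laboratory tables be read as having an undefined baseline. SAP 8.3 cites Section 5.2, which defines none, but 5.3.1 names immunoglobulins under the parent baseline, so this is a cross-reference slip.

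**Conclusion.** The point holds as a gap in the descriptive summaries of secondary measures. It does not touch the primary endpoint, and it is a worthwhile improvement rather than a flaw that undermines the study. Its clearest size is for BEL113750 subjects: a rise of at least 5 SELENA SLEDAI points from Day 0 can appear as no worsening in Table 2.7 and no rebound in Table 2.6. That figure rests on the stated entry scores and does not extend to subjects from BEL112341. The six-subject example and the C3 values are constructed; they show what the summaries cannot distinguish, not what the trial will find. The conclusion also assumes that the unseen shells add no Day 0-based change; no text or title plans one.

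**What to change.** - Keep the parent baseline for rebound and as context.
- Add descriptive change from BEL116027 Day 0 by visit for SELENA SLEDAI, C3/C4, anti-dsDNA, ANA, IgG/IgA/IgM and B cells. Include percent change and shifts only where already defined, and percent change only where the Day 0 value is non-zero. BLyS is not sampled at Day 0 and stays as planned.
- Show this for the holiday and control groups. Show it for the long-term discontinuation group too, with a footnote that these subjects may have been off belimumab for up to 8 weeks before entry.
- Give SELENA SLEDAI an explicit Day 0 row, labelled differently from the parent Baseline.
- State which baseline Table 3 and Tables 1.14 and 1.15 show. The SELENA SLEDAI categories 0, 1, 2, 3 cover neither parent scores of 8 or more nor long-term discontinuation scores above 3 at Day 0, so extend them.
- As editorial corrections only, repair the Section 5.2 reference in SAP 8.3 and distinguish Tables 5.18 and 5.19 from 5.16 and 5.17, whose titles they repeat.

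The cost is a few descriptive tables and some wording. Day 0 and Week 24 assessments are already scheduled (protocol Table 2). Some Day 0 values would come from feeder data, and BEL114333 was not fully cleaned at extraction (SAP 5.3.1 footnotes), so the new tables need a footnote saying so.
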